6.14.3.3.2. Pancreatitis Events

Summaries of adjudicated and investigator-reported pancreatic events will be provided by treatment. Detailed searching criteria can be found in [Appendix 3](#).

Treatment emergent adjudicated-confirmed pancreatitis will be considered as an AESI. Listing of participants with adjudicated pancreatitis may be provided if deemed necessary.

6.14.3.4. Gastrointestinal Safety

6.14.3.4.1. Nausea, Vomiting, and Diarrhea

Summaries and analyses for incidence and severity of nausea, vomiting (including “vomiting” and “vomiting projectile”), diarrhea (including “diarrhea” and “diarrhoea”), and 3 events combined, will be provided by each treatment group.

Summary of the prevalence over time for nausea, vomiting, and diarrhea will also be presented.

Time to the onset of nausea, vomiting, and diarrhea will be plotted.

6.14.3.4.2. Severe Gastrointestinal Events

Severe gastrointestinal (GI) adverse events will be captured with the AE-CRF form and serious cases will be captured with the SAE form. The PTs in the GI SOC MedDRA version at the time of database locks will be used to identify GI AEs, and only the PTs with serious/severe treatment-emergent cases will be considered as AESIs.

The counts and percentages of participants with severe/serious treatment-emergent GI events will be summarized by treatment.

6.14.3.5. Hepatic Safety

6.14.3.5.1. Hepatobiliary Disorders

Severe/serious treatment-emergent hepatobiliary disorders will be considered as AESI. The counts and percentages of participants with treatment-emergent potentially drug-related hepatic

disorders will be summarized by treatment using the MedDRA PTs. Detailed searching criteria can be found in [Appendix 3](#).

A listing of participants with treatment emergent hepatobiliary disorders may be provided if deemed necessary.

6.14.3.5.2. Liver Enzymes

Analyses for laboratory analyte measurements are described in Section [6.14.6](#). This section describes additional analyses of liver enzymes.

The counts and percentages of participants with the following elevations in hepatic laboratory tests at any time during the treatment period and during the entire study including follow up period will be summarized between treatment groups:

- The counts and percentages of participants with an alanine aminotransferase (ALT) measurement ≥ 3 times (3x), 5 times (5x), and 10 times (10x) the Covance ULN will be summarized for all participants with a postbaseline value and for subsets based on various levels of baseline value.
 - participants whose nonmissing maximum baseline value is ≤ 1 x ULN
 - participants whose maximum baseline is > 1 x ULN, and
 - participants whose baseline values are missing.
- The counts and percentages of participants with an aspartate aminotransferase (AST) measurement ≥ 3 x, 5x, and 10x the Covance ULN during the treatment period will be summarized for all participants with a postbaseline value and for subsets based on various levels of baseline, as described above for ALT.
- The counts and percentages of participants with a total bilirubin (TBL) measurement ≥ 2 x the Covance ULN during the treatment period will be summarized for all participants with a postbaseline value, and subset into 4 subsets:
 - participants whose nonmissing maximum baseline value is ≤ 1 x ULN
 - participants whose maximum baseline is > 1 x ULN, but < 2 x ULN
 - participants whose maximum baseline value is ≥ 2 x ULN, and
 - participants whose baseline values are missing.
- The counts and percentages of participants with a serum alkaline phosphatase (ALP) measurement ≥ 2 x the Covance ULN during the treatment period will be summarized for all participants with a postbaseline value and for the subsets described above to TBL.

Maximum baseline will be the maximum non-missing observation in the baseline period. The maximum value will be the maximum non-missing value from the postbaseline period. Planned and unplanned measurements will be included.

6.14.3.6. Hypoglycemia

The following categories in accordance with the 2019 American Diabetes Association position statement on glycemic targets (ADA 2019b) will be defined in the database.

Glucose alert value (Level 1):

- **Documented symptomatic hypoglycemia** is defined as any time a patient feels that he/she is experiencing symptoms and/or signs associated with hypoglycemia, and has a blood glucose (BG) level of <70 mg/dL (<3.9 mmol/L).
- **Documented asymptomatic hypoglycemia** is defined as any event not accompanied by typical symptoms of hypoglycemia, but with a measured BG <70 mg/dL (<3.9 mmol/L).
- **Documented unspecified hypoglycemia** is defined as any event with no information about symptoms of hypoglycemia available, but with a measured BG <70 mg/dL (<3.9 mmol/L).

Documented Clinically Significant Hypoglycemia (Level 2):

- **Documented symptomatic hypoglycemia** is defined as any time a participant feels that he/she is experiencing symptoms and/or signs associated with hypoglycemia and has a BG level of <54 mg/dL (<3.0 mmol/L).
- **Documented asymptomatic hypoglycemia** is defined as any event not accompanied by typical symptoms of hypoglycemia but with a measured BG <54 mg/dL (<3.0 mmol/L).
- **Documented unspecified hypoglycemia** is defined as any event with no information about symptoms of hypoglycemia available but with a measured BG <54 mg/dL (<3.0 mmol/L).

Severe Hypoglycemia (Level 3):

- **Severe hypoglycemia** is defined as an episode with severe cognitive impairment requiring the assistance of another person to actively administer carbohydrate, glucagon, or other resuscitative actions. These episodes may be associated with sufficient neuroglycopenia to induce seizure or coma. Plasma glucose (PG) measurements may not be available during such an event, but neurological recovery attributable to the restoration of PG to normal is considered sufficient evidence that the event was induced by a low PG concentration.

Other hypoglycemia categories:

- Nocturnal hypoglycemia is defined as any hypoglycemic event that occurs between bedtime and waking.

If a hypoglycemic event meets the criteria of severe, the event would specifically be collected as a SAE. Serious hypoglycemia are defined by pharmacovigilance criteria and will also be captured with a SAE form.

To avoid duplicate reporting, all consecutive hypoglycemic events occurring within a 1-hour period will be considered to be a single hypoglycemic event.

Both the incidence (percent of participants experiencing ≥ 1 episode) and the rate (episodes/participant/year) of level 2 or level 3 hypoglycemia, and level 3 hypoglycemia will be reported by treatment group.

[figure not shown]
Severe/serious hypoglycemia will be considered as AESIs. The summaries of severe/serious hypoglycemia will be provided by treatment group. A listing of all events of severe hypoglycemia may be provided, if deemed necessary. This listing will provide treatment allocation, clinical characteristics of the hypoglycemic event, and concomitant antihyperglycemic medications.

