9.2. Sample Size Determination

Approximately 3429 participants will be screened to achieve 2400 randomly assigned to study intervention (600 participants per intervention group).

The sample size determination assumes that evaluation of superiority of 10-mg tirzepatide and tirzepatide 15 mg to placebo will be conducted in parallel, each at a 2-sided significance level of 0.025 using a 2-sample t-test. Additionally, a difference of at least 11% mean body weight percentage reduction from randomization at 72 weeks for 10-mg tirzepatide and/or tirzepatide 15 mg compared with placebo, a common SD of 10%, and a dropout rate of 25% are assumed for statistical power calculations. Under the assumptions above, randomizing 2400 participants in a 1:1:1:1 ratio to tirzepatide 5 mg (600), tirzepatide 10 mg (600), tirzepatide 15 mg (600), and placebo (600) provides more than 90% power to demonstrate superiority of tirzepatide 10 mg and/or 15 mg to placebo.

The chosen sample size and randomization ratio also provides >90% power to establish superiority of 10-mg tirzepatide and 15-mg tirzepatide doses to placebo in term of percentage of participants achieving at least 5% body weight reduction at 72 weeks, conducted in parallel using a Fisher's exact test, each at a 2-sided significance level of 0.025, assuming 25% placebo-treated participants and 90% tirzepatide-treated participants achieving the goal and a dropout rate of 25%.

In addition, assuming that approximately 60% of the randomized population will have prediabetes, the study sample size will also provide more than 90% power to demonstrate superiority of tirzepatide (all doses combined) over placebo in terms of delaying the onset of diabetes for participants with prediabetes at study entry. It is based on the following assumptions: 1.6% (corresponding to annual hazard rate of 0.54%) of participants randomized to tirzepatide and 6% of participants randomized to placebo (corresponding to annual hazard rate of

2.1%) will progress to diabetes during the 3-year period; 49% of participants will drop out (corresponding to annual drop-out rate of 22%) during the same period; and the test will be conducted at a 2-sided significance level of 0.05.

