10.3.1. Special Safety Topics

10.3.1.1. Hypoglycemia

Upon ICF signing, all participants will be educated about signs and symptoms of hypoglycemia, how to treat hypoglycemia, and how to collect appropriate information for each episode of hypoglycemia.

Hypoglycemia may be identified by spontaneous reporting of symptoms from participants (whether confirmed or unconfirmed by simultaneous glucose values) or by blood glucose (BG) samples collected during study visits.

All participants who develop diabetes during the study will be provided with glucometers. Participants without diabetes may, at the investigator's discretion, be given glucometers to assist in the evaluation of reported symptoms consistent with hypoglycemia. Participants receiving glucometers will be provided a diary to record relevant information (for example, glucose values, symptoms).

Hypoglycemic episodes will be recorded on a specific eCRF and should not be recorded as AEs unless the event meets serious criteria. If a hypoglycemic event meets severe criteria (see definition below), it should be recorded as serious on the AE and SAE eCRFs, and reported to Lilly as an SAE.

Investigators should use the following definitions and criteria when diagnosing and categorizing an episode considered to be related to hypoglycemia (the plasma Glucose values in this section refer to values determined by a laboratory or International Federation of Clinical Chemistry and Laboratory Medicine blood-equivalent glucose meters and strips) in accordance with the 2019 American Diabetes Association position statement on glycemic targets (American Diabetes Association 2019a):

Glucose Alert Value (Level 1):

- **Documented symptomatic hypoglycemia** is defined as any time a patient feels that he or she is experiencing symptoms and/or signs associated with hypoglycemia and has a BG level of <70 mg/dL (≤ 3.9 mmol/L).
- **Documented asymptomatic hypoglycemia** is defined as any event not accompanied by typical symptoms of hypoglycemia, but with a measured BG <70 mg/dL (≤ 3.9 mmol/L).
- **Documented unspecified hypoglycemia** is defined as any event with no information about symptoms of hypoglycemia available, but with a measured BG <70 mg/dL (≤ 3.9 mmol/L).

Clinically Significant Hypoglycemia (Level 2):

- **Documented symptomatic hypoglycemia** is defined as any time a participant feels that he or she is experiencing symptoms and/or signs associated with hypoglycemia and has a BG level of <54 mg/dL (<3.0 mmol/L).

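### The pooled Level 2-or-3 hypoglycemia rate by arm depends on who had a glucose reading, and outside visits that depends mainly on diabetes onset or symptom reports

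*SAP*

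**What the plan says.** SAP 6.14.3.6 reports incidence and "the rate (episodes/participant/year) of level 2 or level 3 hypoglycemia, and level 3 hypoglycemia will be reported by treatment group". Level 2 appears only pooled with Level 3, while Level 3 also has its own line. Under SAP 6.14 the analysis uses the safety analysis set, which is everyone randomized and dosed. It is not split by diabetes status, meter possession or source of the reading.

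All three Level 2 categories require a glucose value. Even the asymptomatic one is an event "not accompanied by typical symptoms of hypoglycemia but with a measured BG <54 mg/dL". Level 3 is defined clinically: "Plasma glucose (PG) measurements may not be available during such an event".

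Protocol 10.3.1.1 gives three routes to a reading:

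- After diabetes onset: "All participants who develop diabetes during the study will be provided with glucometers".
- Without diabetes, participants may, at the investigator's discretion, "be given glucometers to assist in the evaluation of reported symptoms consistent with hypoglycemia".
- Events may also be found from reported symptoms "or by blood glucose (BG) samples collected during study visits".

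Protocol 4.1.2.2 stops scheduled OGTTs once diabetes is diagnosed. Protocol 9.2 plans for diabetes onset over 3 years in "1.6% (corresponding to annual hazard rate of 0.54%) of participants randomized to tirzepatide and 6% of participants randomized to placebo".

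**The concern.** The trial enrols people without diabetes, so at the start nobody has a study glucometer. For most participants most of the time, a glucose below 54 mg/dL outside a visit leaves no record. The people who do get a meter are selected after randomization, by developing diabetes or by reporting symptoms. Treatment is expected to reduce the first, and it may change the second.

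A rate per participant-year by arm invites the reader to compare how often glucose falls below 54 mg/dL on drug and on placebo. With this data collection, the figure mixes any drug effect with access to measurement. A real excess on tirzepatide could be masked because more placebo participants hold meters. A null effect could look like an excess if symptoms lead to more meters on tirzepatide. Time after onset is also when other glucose-lowering drugs may be started (Protocol 6.5), so metered and unmetered time differ in more than detection.

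**Working it through.** **Inputs (Protocol 9.2).** Three-year diabetes onset of 6% on placebo and 1.6% on tirzepatide, 49% dropout over 3 years, and about 60% of participants with prediabetes.

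**Step 1: reproduce the plan's hazards.** Hazard = −ln(1 − p)/3.

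- Placebo: −ln(0.94)/3 = 0.0206 per year (stated 2.1%).
- Tirzepatide: −ln(0.984)/3 = 0.0054 per year (stated 0.54%).
- Dropout: −ln(0.51)/3 = 0.224 per year (stated 22%).

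All three match.

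**Step 2: share of person-time after diabetes onset**, taken as the time with a routinely supplied meter. With onset hazard h, dropout hazard d and horizon T years:

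- In-study time per participant: A = (1 − e^(−dT))/d
- Diabetes-free in-study time: B = (1 − e^(−(h+d)T))/(h + d)
- Share after onset = (A − B)/A

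Prediabetes cohort, T = 176/52.18 = 3.373 years, A = 2.3656:

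- Placebo: B = 2.2951, share = 0.0298, or 3.0%.
- Tirzepatide: B = 2.3469, share = 0.0079, or 0.8%.

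Without dropout the shares are 3.4% and 0.9%. The gap between arms is thus 2.2 to 2.5 percentage points.

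All randomized, T = 72/52.18 = 1.380 years, assuming onset only in the 60% with prediabetes: 0.6 × 1.34% = 0.8% on placebo and 0.6 × 0.35% = 0.2% on tirzepatide, a gap of about 0.6 points.

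**Step 3: effect on the comparison.** Let c be the share from step 2 for the 176-week cohort, and g the share of the remaining time covered by discretionary meters. The documents do not give g, so the values below are assumptions. Assume also that the true out-of-visit Level 2 rate is the same in both arms and the same before and after onset. The captured share is c + (1 − c)g.

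| g placebo | g tirzepatide | captured, placebo | captured, tirzepatide | apparent ratio, true ratio 1 |
|---|---|---|---|---|
| 0 | 0 | 3.0% | 0.8% | 0.26 |
| 5% | 5% | 7.8% | 5.7% | 0.73 |
| 10% | 10% | 12.7% | 10.7% | 0.84 |
| 25% | 25% | 27.2% | 25.6% | 0.94 |
| 50% | 50% | 51.5% | 50.4% | 0.98 |
| 5% | 10% | 7.8% | 10.7% | 1.37 |
| 10% | 20% | 12.7% | 20.6% | 1.63 |

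The ratio covers meter-detected events only. Visit samples are left out.

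**Step 4: how many people contribute post-onset time.** Expected onsets under dropout over 3 years = n × h/(h + d) × (1 − e^(−3(h+d))). Of 2400 × 0.6 = 1440 with prediabetes, 360 are on placebo and 1080 on tirzepatide. This gives 15.8 on placebo and 12.6 on tirzepatide, or about 4 per dose.

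**The case against.** **Size.** A reader might infer that the rate is strongly understated, because the denominator is many times the routinely metered time. The documents do not support that. They give no true Level 2 rate and no frequency of discretionary meters. Captured shares in the table run from about 1% to about half, depending only on an assumed g. Few events would be missed if Level 2 is rare in people not taking glucose-lowering drugs.

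**Denominator.** A reader might also infer that the rate is taken over everyone's full follow-up. SAP 6.14.3.6 does not define the person-time, and where rates are modelled SAP 6.14 uses active-treatment days. The ascertainment problem remains under either window.

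**Direction.** The 0.26 is an extreme case, not a forecast of the reported statistic. The planned rate also includes visit samples, and any route equal across arms pulls the ratio toward 1. A laboratory value from outside the study visits could count too. The absolute gap in routine coverage is small, and the net direction is not fixed.

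**Importance.** The SAP names no test for Level 2, no endpoint controlled for type 1 error is involved, and the event of special interest is severe or serious hypoglycemia.

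**A tempting repair.** Restricting the Level 2 rate to post-diagnosis time would condition on an outcome that treatment is expected to change, with about 16 placebo participants and 4 per dose contributing. Under Protocol 4.1.2.3 the laboratory-based onset date is normally the first abnormal value, which can precede confirmation and the meter. The documents do not say that the meter issue date is recorded.

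All of this stands. It limits what can be claimed about size and direction, and it rules out that repair. It does not remove the dependence of the pooled rate on who could be measured.

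**Conclusion.** The point holds for Level 2 and not for Level 3. Out-of-visit Level 2 events are undercounted by an unknown amount. Routine meters cover about 3.0% of placebo and 0.8% of tirzepatide person-time over 176 weeks in the prediabetes cohort, and about 0.8% and 0.2% over 72 weeks in all randomized. With equal true rates, the apparent ratio of meter-detected events could fall below 1 or rise above it, so the pooled rate does not support a comparison of arms.

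The coverage figures rest on the protocol's planning hazards and dropout, on a meter being in hand from onset, and, for 72 weeks, on onset occurring only in those with prediabetes. The ratios rest also on the assumed discretionary coverage. This is a worthwhile reporting change to a safety summary and does not touch the primary or key secondary conclusions.

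**What to change.** In SAP 6.14.3.6:

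1. Keep Level 3 incidence and rate as planned, over the whole treatment group.
2. Report Level 2 separately from Level 3 and by source.
   - (a) Scheduled fasting visit samples below 54 mg/dL, by arm. The sampling schedule is the same in all arms, so this is the comparison least dependent on meter access. Put post-load OGTT samples on their own line, because OGTTs stop after a diabetes diagnosis.
   - (b) Out-of-visit readings as counts and percentages by arm, shown descriptively before and after diabetes diagnosis, with no per-year rate used to compare arms.
3. Label any pooled Level 2-or-3 rate as dependent on ascertainment.

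The cost is SAP wording and one more table, with few events and wide intervals in (b). No change to clinical management is needed.

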6.14.3.7. Immunogenicity

6.14.3.7.1. Definitions of Sample ADA Status

At a high level, an individual sample is potentially examined multiple times, in a hierarchical procedure, to produce a sample anti-drug antibodies (ADA) assay result and potentially multiple cross-reactive antibodies assay results and multiple neutralizing antibodies (NAb) assay results. The cut points used, the drug tolerance of each assay, and the possible values of titers are operating characteristics of the assay.

[Figure GPHK.6.2](#) details a flow chart that reflects the multitiered testing approach.

Abbreviations: ADA = anti-drug antibodies; CP = cut point; GIP = glucose-dependent insulinotropic polypeptide; GIPR = glucose-dependent insulinotropic polypeptide receptor; GLP-1 = glucagon-like peptide-1; GLP-1R = glucagon-like peptide-1 receptor; LY = LY3298176; NAb =neutralizing antibodies.

Figure GPHK.6.2. Flowchart of immunogenicity multitiered testing approach.

Table GPHK.6.7 outlines results as reported from Tier 2a of the multitiered testing approach. Tier 4 results are reported similarly.

Table GPHK.6.7. Sample Anti-Drug Antibodies (ADA) Assay Results

Sample Laboratory Result	Explanation
Detected	ADA are detected and confirmed.
Not Detected	The raw result as reported from the laboratory indicates not detected. The clinical interpretation of such results depends other factors (see Table GPHK.6.8).
NO TEST, QNS, etc.	Sample exists but was unevaluable by the assay.

Abbreviations: ADA = anti-drug antibodies; QNS = quantity not sufficient.

It can be the case that the presence of high concentrations of tirzepatide will affect immunoassays, and conversely high levels of antibodies may affect the measurement of tirzepatide concentration. Thus, a tirzepatide drug concentration, assessed from a sample drawn at the same time as the ADA sample, plays a key role in clinical interpretation of a sample when the laboratory results is Not Detected (see [Table GPHK.6.8](#)).

Table GPHK.6.8. Sample Clinical Anti-Drug Antibodies (ADA) Interpretation Results

Sample Clinical Interpretation	Explanation
ADA Present	ADA assay result is Detected
ADA Not Present	ADA assay result is Not Detected and drug concentration is at a level that has been demonstrated to not interfere in the ADA detection method (that is, drug concentration is below the assay's drug tolerance level). For participants receiving placebo, drug concentration is not assessed and is assumed to be below the assay's drug tolerance level. If drug concentration was planned but is not available for a treatment-period sample, a Not Detected sample will be declared ADA Not present.
ADA Inconclusive	ADA assay result is Not Detected but drug concentration in the sample is at a level that can cause interference in the ADA detection method.
ADA Missing	ADA sample not drawn, QNS, not tested, etc., causing there to be no laboratory result reported or the result is reported as "no test."

Abbreviations: ADA = anti-drug antibodies; QNS = quantity not sufficient.

All ADA present samples will be evaluated for cross-reactive glucose-dependent insulinotropic polypeptide (GIP), cross-reactive glucagon-like peptide-1 (GLP-1), Nab LY3298176 (LY) on glucose-dependent insulinotropic polypeptide receptor (GIP-R), and Nab LY on glucagon-like peptide-1 receptor (GLP-1R). If cross-reactive GIP is detected, Nab GIP on GIP-R is evaluated. If cross-reactive GLP-1 is detected, Nab GLP on GLP-1R is evaluated ([Figure GPHK.6.2](#)).

Similar terminology to [Table GPHK.6.8](#) applies for each type of cross-reactive and Nab assay. Importantly, each of these are distinct assays and, in general, have different assay operating characteristics.

The following are considered inconclusive for the NAb result:

- NAb LY on GIP-R: if NAb result is not detected, and pharmacokinetic (PK) concentration is \geq drug tolerance limit of the NAb LY on GIP-R assay
- NAb LY on GLP-1R: if NAb result is not detected, and PK concentration is \geq drug tolerance limit of the NAb LY on GLP-1R assay
- NAb GIP on GIP-R: if NAb result is not detected, and PK concentration is \geq drug tolerance limit of the NAb GIP on GIP-R assay
- NAb GLP-1 on GLP-1R: if NAb result is not detected, and PK concentration is \geq drug tolerance limit of the NAb GLP-1 on GLP-1R assay

To mitigate inconclusive cross-reactive NAb interpretations against nGIP and nGLP-1 due to potential tirzepatide concentrations greater than or equal to the drug tolerance limit of the cross-reactive NAb assays (Tier 4c and 4d, respectively), an *in silico* method utilizing results from Tiers 2b and 2c, Tiers 4a and 4b, and tirzepatide concentrations is introduced. The *in silico* method is outlined in [Table GPHK.6.9](#).

Table GPHK.6.9. In Silico Classification for Cross-Reactive NAB

In Silico Classification	Cross-reactive Binding ADA Result	NAb Result	Circulating Tirzepatide Level (ng/mL)	In Silico Cross-reactive NAB Interpretation
Cross-reactive NAb to nGIP	Tier 2b: "Not Detected"	Tier 4a: "Not Detected" or Tier 4a: "Detected" or N/A or Missing	Any Value or Missing	Not Present
	Tier 2b: "Detected"	Tier 4a: "Not Detected"	<drug tolerance limit of Tier 4a assay	Not Present
	Tier 2b: "Detected"	Tier 4a: "Not Detected"	\geq drug tolerance limit of Tier 4a assay	Inconclusive
	Tier 2b: "Detected"	Tier 4a: "Detected"	<drug tolerance limit of Tier 4a assay	Present
	Tier 2b: "Detected"	Tier 4a: "Detected"	\geq drug tolerance limit of Tier 4a assay	Present
Cross-reactive NAb to nGLP-1	Tier 2c: "Not Detected"	Tier 4b: "Not Detected" or Tier 4b: "Detected" or NA or Missing	Any Value or Missing	Not Present
	Tier 2c: "Detected"	Tier 4b: "Not Detected"	<drug tolerance limit of Tier 4b assay	Not Present

In Silico Classification for Cross-Reactive NAb

In Silico Classification	Cross-reactive Binding ADA Result	NAb Result	Circulating Tirzepatide Level (ng/mL)	In Silico Cross-reactive NAb Interpretation
Cross-reactive NAb to nGLP-1	Tier 2c: "Detected"	Tier 4b: "Not Detected"	≥drug tolerance limit of Tier 4b assay	Inconclusive
	Tier 2c: "Detected"	Tier 4b: "Detected"	<drug tolerance limit of Tier 4b assay	Present
	Tier 2c: "Detected"	Tier 4b: "Detected"	≥drug tolerance limit of Tier 4b assay	Present

Abbreviations: ADA = antidrug antibodies; GIP = glucose-dependent insulinotropic polypeptide; GLP-1 = glucagon-like peptide-1; NAb = neutralizing antibodies; nGIP = native glucose-dependent insulinotropic polypeptide; nGLP-1 = native glucagon-like peptide-1; Tier 2b = cross-reactive ADA to nGIP; Tier 4a = NAb LY (tirzepatide) on GIP receptor; Tier 4b = NAb LY (tirzepatide) on GLP-1 receptor.

Note: Only the drug tolerance limits of the Tier 4a and 4b assays are used for in silico classifications as they are lower than the drug tolerance limits of the Tier 2b and 2c assays, respectively.

